#### **4.11 Referral to another centre for HSCT**

In the most part for this trial, consolidation chemotherapy and HSCT will occur at a single hospital site, and therefore intervention delivery and follow up data collection will be seamless. In cases where chemotherapy and HSCT are delivered at different sites, trial follow up may require collaboration with the transplanting centre.

Where the transplanting centre is also open to PROPEL, the recruiting centre should notify the PROPEL trials office as soon as possible and prior to HSCT, and a hospital transfer CRF should be completed. The PROPEL trials office will contact the transplanting centre and organise the participant to be transferred via the PROPEL database. Although informed consent is an ongoing process, the original signed informed consent form will remain valid and does not require re-signing at the transplant centre at the point of transfer. The PROPEL trial office can advise if your nearest transplant centre is also open to PROPEL.

Where the transplanting centre is not open to PROPEL, post HSCT follow-up will involve close communication between the referring and transplant hospital. Sites should make every effort to collect data and questionnaires remotely where the participant does not return to the referring hospital at the relevant timepoint. If physical outcome assessments cannot be collected, the reason for this should be documented on the relevant case report form. PROPEL specialists will be available to contact for advice, should the transplanting hospital have any questions about the care plan in place for participants on the PPCP arm.

#### **4.12 Post-randomisation withdrawals, exclusions and moves out of region**

Participants may be discontinued from the trial treatment and/or the trial at any time without prejudice. Unless a participant explicitly withdraws their consent, they should be followed-up wherever possible and data collected as per the protocol until the end of the trial.

Patients may be withdrawn from their trial allocation at the discretion of the Investigator and/or Trial Management Committee. If a patient withdraws from their trial allocation, either by their choice or at the discretion of the investigator, they must be followed up in accordance with the protocol. For patients who are lost to follow-up, follow-up data should

continue to be collected from hospital or GP records, these patients should not be automatically withdrawn from the trial.

Patients moving away from the region of the local site should NOT be withdrawn from the trial. Should this occur, please contact the PROPEL Trial Office with the relevant details, and they will endeavour to assign the patient's follow-up to a site close to their new location.

#### **4.13 Co-enrolment into other trials**

The NIHR AML group including PPI are involved in the development of new protocols for treatment of AML. The CIs of these trials will be asked whether PROPEL can also be offered to patients in the treatment trials. As a non-CTIMP, it is expected that co-enrolment to PROPEL will be permitted. Patients randomised into PROPEL can be enrolled into other studies as long as this has been agreed with the TMG and they do not affect the PROPEL outcomes. Once agreed, these trials will be added onto a rolling list of trials permitted for co-enrolment.

#### **4.14 Site Staff Training**

PI's may be drawn from a range of health care professionals at participating sites, including haematologists. Nurses/allied healthcare professionals (NAHPs) are also actively encouraged to act as local PIs.

A standardised training package will be given face to face or virtually to nurses and AHPs who are supporting the PPCP for those people randomised to PPCP. Training includes:

- How to recruit and randomise participants
- Collection of data for pre-planning screening and onward referral for specialist services
- Structure of the weekly check-ins including ACT principles and behaviour change techniques to encourage adherence
- Contacting the central PROPEL specialist team for support (when and how to do this)

#### **4.15 End of trial**

The end of study will be defined as last data capture for the last participant, allowing three months after the last visit to return CRFs and answer data queries. The CI will notify the Sponsor, participating sites and REC within 90 days of the end of study, or within 15 days if the study is ended prematurely. The clinical study report will be written within 12 months of the end of study.

## **5 PARALLEL PROCESS EVALUATION**

Guided by the MRC framework for evaluation of complex interventions [45], the mixed methods process evaluation will inform interpretation of trial results and wider implementation of the intervention package. It will provide understanding of the

implementation and functioning of the intervention, including intervention personalisation, in context. The PROPEL intervention model of delivery is through a combination of locally delivered aspects and remotely delivered aspects of the different components of the intervention. The process evaluation will assess this delivery model and consider the feasibility and practicalities of implementing this model of prehabilitation in practice.

**Aims:** To investigate issues that may affect the delivery and outcomes of the intervention and assess the feasibility of implementing the intervention widely in the NHS

**Objectives:**

1. To investigate intervention delivery fidelity and impact dose of the PROPEL intervention model.
2. To investigate patients', local site PROPEL Trained HCPs', managers', remote delivery practitioners and central PROPEL specialist team experiences of the intervention, how and why the intervention did or did not facilitate change among participants, at a sample of 6 sites, and
3. To explore how the intervention delivery was implemented by the remote delivery practitioners at the sample of 6 sites and how that implementation affected how the intervention package was delivered and received.

**Design**

A theoretically informed mixed methods process evaluation consisting of a fidelity and intervention dose assessment across all intervention sites, measurement of any behaviour change differences between intervention and control groups across all sites, and a qualitative interview study focused on six sites.

**Theoretical framework**

The multiphasic, multi-modal prehabilitation package intervention (PPCP) is informed by theoretically informed behavioural change determinants such as motivation and the principles of Acceptance and Commitment Therapy (ACT), which promotes psychological flexibility. These determinants associated behaviour techniques and principles will inform the study's intervention logic model. The behaviour change techniques can be identified in the Behaviour Change Taxonomy (BCT) [46] which focuses on the techniques or active ingredients in interventions that can lead to the desired behaviour changes. The Theoretical Domains Framework (TDF) [47] is associated with the BCT, and in turn is associated with the COM-B framework [24] and Behaviour Change Wheel [48]. This will broaden our view from individual behaviour change to interactions with systems in order to frame our exploration of intervention implementation.

We will use the evaluation framework, as a lens to explore not only whether the intervention package works for the patients as hypothesised but also to identify barriers and facilitators

to implementing the intervention at different levels of the organisation. To do this we will explore the different layers of the context in which they receive the intervention. These include the existing structures of the organisation where the intervention is delivered, the management of the clinical service and any changes made to deliver both the remote and local components of the intervention, the experiences of the local PROPEL Trained HCP and the remote intervention therapists and the central PROPEL specialist team in delivering the intervention to the patient.

### **Samples for different components of the process evaluation**

The investigation of intervention delivery fidelity and impact of the dose of the PROPEL intervention model (objective 1) has been described in section 4.8 'Fidelity' above.

All study participants will take part in an assessment of the intervention's underlying behaviour change techniques and ACT principles (in particularly psychological flexibility) to assess whether the intervention group was any different to the control group. The measures are selected to measure change expected with the intervention.

#### ***Psychological Flexibility***

The 8-item brief CompACT will be used as a measure of psychological flexibility [23].

#### ***Motivation***

The trial-adapted COM-B questionnaire item on Motivation will be used to measure motivation for each of the intervention components [24]. There will be 3 items in total (one for each intervention component).

#### **Nutrition Impact Symptoms (NIS)**

Modified unvalidated questionnaire based on the Omlin nutrition impact symptom (NIS) checklist [49] will be used to measure the impact of NIS on dietary intake. It includes 10 symptoms and 2 additional questions about food access on PPI request. Instead of severity of symptoms (which will be captured by adverse events) frequency of occurrence has been added to quantify burden more accurately. The questionnaire has been reviewed by 8 AML patients and 4 topic specialists for ease of understanding and relevance with updates made.

Six sites will participate in a more detailed evaluation (objective 2 and 3). They will be purposively selected to ensure the sample includes the following characteristics: whether or not they have a transplant service, previous routine provision of prehabilitation or not, and serving different populations (e.g., urban/rural, mixes of socio-economic areas and mix of ethnic groups). Two sites will be selected during the pilot phase and the remaining 4 in the main study. Having two sites in the pilot phase could allow opportunity to assess the feasibility of the planned data collection. Data from all six sites will be used in the final evaluation.

### **Sample recruitment and consenting for interview participants at the detailed evaluation sites.**

Patient participants from each arm of the study at the selected process evaluation study sites will be given the opportunity to indicate they are willing to be contacted about the process evaluation when they are consented for the main study. If so, they will provide their contact details for this purpose. They will be informed that they may not be contacted as only a few people from each of only a few sites are needed. We will purposively select from those potential participants at each site and contact them to see if they would like to take part. We will provide potential participants with more detailed information about what will be involved, and they will be given the opportunity to ask questions. If they agree to take part, an interview will be arranged, and informed consent will be taken by the researcher conducting the interviews. This may be on the same day or beforehand. The patient sample will be purposively selected to achieve a sample of up to 4 participants per arm at each of the 6 sites. The participant sample will be selected to include a range of characteristics such as age, gender, ethnicity. Patients will be asked whether they wish a family member or key supporting person to be involved in the interviews or not. For those who do want this, the family member/key supporting person will also be given study information, the opportunity to ask questions and provide consent for participation in the interview.

The site research team and PI will be asked to identify the PROPEL Trained local HCPs involved in intervention delivery (up to 3) and key managers (up to 3) involved in implementation of the intervention. Although participation will be voluntary, to alert staff to the possibility, the site PI and research team will be asked to let their local teams know that they may be interviewed about their experiences of the intervention as part of the study, from the outset. This information may also be reiterated during the site initiation. The research team will approach the selected potential participants to obtain informed consent.

Members of the multidisciplinary specialist team delivering remote components of the interventions at the six sites will be interviewed. They will be selected to include up to three practitioners involved in each of wellbeing, diet and physical activity. Members of the research team supervising interventions will also be interviewed. Informed consent will be gained from all participants.

### **Mitigating risk:**

We do not anticipate any serious adverse events arising from participation in interviews for the process evaluation. However, it is possible participants, particularly patients and their relatives may experience distress when talking about their experiences. Participants will be given the opportunity to take a break or end the interview should this happen. Participants will be referred to their clinical team, with their permission, should any areas that require further support be identified. Relatives will be signposted to sources of support such as their GP or charities supporting relatives of patients with cancer.

Interviewer's will also be given the opportunity to access debrief sessions, should they require it, if they find the interviews distressing and emotive.

Most interviews are expected to take place over the phone or via video call. If required, a face-to-face interview will be facilitated where possible, and would be subject to UoW lone working policy and relevant risk assessment.

### **Data collection**

Data collection for the fidelity and intervention dose is described in section 4.8 Fidelity above. Data collection for the mechanisms of action will be through the patient completed CRF pre-, during-, and post-intervention.

The intervention description, logic model and underpinning theories including those underpinning Acceptance and Commitment Therapy (ACT) [32], the Theoretical Domains Framework (TDF) and associated Behaviour Change Taxonomy (BCT) [50] will inform data collection and analysis of the process evaluation interviews at sites and with members of the delivery teams. The interview topics for exploration with participants will be informed by the evaluation framework and will therefore cover perspectives of the intervention and how it worked (or did not work) and how it was implemented from patients', clinicians', managers', and multidisciplinary hub team members' viewpoints.

Starting during the internal pilot phase, at each site semi-structured online/telephone or face to face interviews will be conducted with participants.

### **Data analysis**

To assess delivery fidelity, check list scores and the proportion of sessions delivered will be summarised for the different components of the intervention (nutrition, physical activity, emotional well-being and weekly behavioural support) alongside reasons for non-delivery. Self-reported participant adherence to the different components, logbook completion, and discussion of behaviour change techniques will be summarised based on data collected during the weekly check-ins. Intervention dose will be calculated for each component using the data outlined in Table 2. Associations between key study outcomes and adherence, and dose will be explored. A comparative analysis of behavioural mechanisms will be conducted to assess differences between study and intervention group, and if appropriate mediation analysis will explore whether differences in these mechanisms are related to study outcomes.

We will use data from the interviews to describe the approach to implementation taken at each of the six sites. We will conduct a thematic analysis of the qualitative interview data using an abductive approach. An analysis framework [47] will be iteratively developed. Initial development will be based on the study evaluation framework. Interview data will be coded, categorised and grouped into themes. These will be assessed for fit and explanatory value within the existing framework themes or will be used to create new themes within the framework. We will also analyse data from each site and across all sites, to enable

identification of differences and similarities and how the approach to implementation may have impacted on the delivery of or outcomes of the interventions.

Fidelity, adherence, dose and behavioural mechanism results will be narratively combined with the qualitative interview findings to inform interpretation of main trial outcomes and the process evaluation's aims and objectives.

### **Dissemination and further implementation**

The process evaluation will include stakeholder meetings to discuss the results with commissioners who will be encouraged to implement prehabilitation should the results show benefit and cost effectiveness. This will help identify what implementation issues are the most important from a commissioner's perspective. The output from these meetings will aim to provide information for non-participating sites who may want to commission these services should the intervention been deemed effective.

## **6 ADVERSE EVENT MANAGEMENT**

### **6.1 Adverse Events (AE)**

An Adverse Event (AE) is defined as any untoward medical occurrence in a participant *participating in a clinical study* and which does not necessarily have a causal relationship with the treatment/intervention.

For the purpose of this study, the following events are regarded as expected AEs and **should not** be reported:

- AE's relating to chemotherapy, HSCT, blood transfusions or standard treatment delivery (outside of the PROPEL intervention). This information, where required, is collected on the treatment CRF's.
- AE's relating to recurrence or progression.
- Procedures which are elective or pre-planned, or for a pre-existing condition.

Any AE's which do not fall into the above categories, are considered as special interest as they may be related to the delivery of the intervention or control, and should be reported on the 'AE of special interest' CRF. Possible examples include musculoskeletal injuries related to exercise, or adverse events during the conduct of physical outcomes assessments.

Any AE's linked to the study outcomes will be collected on the relevant treatment CRF. Recurrence of and/or death from AML are outcome measures of the trial that will be collected via the CRF (the Event Form and Notification of Death Form) and are treated as expected events.

## 6.2 Serious Adverse Events (SAEs)

A Serious Adverse Event is an AE that fulfils one or more of the following criteria:

- Results in death
- Is immediately life-threatening
- Requires hospitalisation or prolongation of existing hospitalisation
- Results in persistent or significant disability or incapacity
- Is a congenital abnormality or birth defect
- Immediate intervention was required to prevent one of the above or is an important medical condition.

For the purpose of this study, the following are regarded as expected SAEs and **should not** be reported on an SAE Form:

- SAE's relating to chemotherapy, HSCT, blood transfusions or standard treatment delivery (outside of the PROPEL intervention). This information is collected on the treatment CRF's.
- SAE's relating to recurrence or progression.
- Procedures which are elective or pre-planned, or for a pre-existing condition.

This is not an exhaustive list and Investigators should use their own judgement when reporting SAEs.

## 6.3 Reporting procedure:

### 6.3.1 Site

Site events that meet the criteria for an SAE, per the protocol, should be reported to WCTU on the SAE form. When completing the form, the Investigator will be asked to confirm the following information:

- full details in medical terms and case description
- event duration (start and end dates, if applicable)
- action taken
- outcome
- grade of severity (categorised using the Common Terminology for Adverse Events (CTCAE) version 5.0) [51].
- causality (i.e. relatedness to intervention), in the opinion of the investigator

On becoming aware that a patient has experienced a SAE, the Investigator (or delegate) must complete, date and sign the SAE Form (blank copies located in the ISF). The form must be sent by email to the Trial Office as soon as possible and no later than 24 hours after first becoming aware of the event.

**To report an SAE, email the SAE form to  
[[contact]](mailto:[contact])**

Patients should be followed up until resolution or stabilisation of the event. Any change of condition or other follow-up information should be reported to WCTU using the method described above as soon as it is available. Follow-up information should be provided on a new SAE form.

### **6.3.2 Trial office (WTCU)**

The Trial Office will report all events that are categorised as Unexpected and Related SAEs to the REC within 15 days of receipt. Details of all Unexpected and Related SAEs will also be reported to Principal Investigators at recruiting sites.

### **6.3.3 Reporting Period**

Details of all SAEs (except those listed in Section 7.2) will be documented and reported from randomisation until 30 days post EOT. This reporting period should be sufficient to capture all SAEs associated with the trial protocol however, if a related SAE is identified after this period, the event should be reported to the Trial Office.

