## **4.4 Randomisation**

Before randomising a participant, written informed consent must have been obtained and confirmation of trial eligibility documented in the patient's medical notes. Baseline assessments should also have been completed prior to randomisation. Where a participant is not eligible to proceed to randomisation post informed consent (i.e. if bone marrow results do not confirm remission), this information should be captured on the screening log.

Randomisation should occur at the end of induction chemotherapy, once remission status has been confirmed, and prior to the first cycle of consolidation chemotherapy.

Sites should log on to the PROPEL randomisation portal to randomise the participant. Sites should access the portal via the link below:

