## 4.9 Schedule of assessments

Visit	1	2	3	4	5	6	7	8
		Consolidation Treatment: To mirror the participant's planned treatment pathway						
Visit Window (No. Weeks ± No. Days)	Baseline*	Cycle 1 (Day 0) -8days	Cycle 2/HSCT -8days	Cycle 3/ HSCT -8days	EOT	3months post EOT	Month 24 (post randomisation anniversary)	Annual follow up (up to 5 years) (post randomisation anniversary)
Informed consent	x							
Medical history	x							
Confirm patient eligibility	x							
Randomisation		x a						
BPUC only: 30minute BPUC appointment		x						
PPCP only: MDT care planning sessions		x	x	x				
PPCP only: Participant check in		x Weekly check in						
Questionnaire booklet	x		x	x	x	x	x	
Health resource use questionnaire			x	x	x	x	x	

Visit	1	2	3	4	5	6	7	8
		Consolidation Treatment: To mirror the participant's planned treatment pathway						
Visit Window (No. Weeks ± No. Days)	Baseline*	Cycle 1 (Day 0) -8days	Cycle 2/HSCT -8days	Cycle 3/ HSCT -8days	EOT	3months post EOT	Month 24 (post randomisation anniversary)	Annual follow up (up to 5 years) (post randomisation anniversary)
PPCP only: Clinical screening questionnaire booklet		x	x	x				
6minute Walk Test	x					x b	x b	
Performance status	x	x	x	x	x	x	x	
SARC-F & Calf circumference	x				x b	x b	x b	
Hand grip strength	x				x b	x b	x b	
Height	x							
Weight	x	x c	x	x	x	x	x	
Food diary e	x d	x ce	x e	x e	x e	x e		
Haematology and biochemistry f	x f	x cf PPCP only	x f PPCP only	x f PPCP only				
Adverse events / complications of treatment			x	x	x			

Visit	1	2	3	4	5	6	7	8
		Consolidation Treatment: To mirror the participant's planned treatment pathway						
Visit Window (No. Weeks ± No. Days)	Baseline*	Cycle 1 (Day 0) -8days	Cycle 2/HSCT -8days	Cycle 3/ HSCT -8days	EOT	3months post EOT	Month 24 (post randomisation anniversary)	Annual follow up (up to 5 years) (post randomisation anniversary)
Review participant logbook			x g PPCP only	x g PPCP only	x g PPCP only			
Onward referrals		x As required h						
Survival status						x	x	x

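### The SAE reporting period is described as long enough for the trial's own procedures, but all three scheduled 6-minute walk tests fall outside it.

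*Protocol*

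**What the plan says.** Protocol section 6.3.3 states that SAEs, apart from the exempt ones, "will be documented and reported from randomisation until 30 days post EOT". It adds that this should be enough to pick up every SAE connected with the protocol, and makes one exception: "if a related SAE is identified after this period, the event should be reported to the Trial Office". Section 6.3.1 lists what the investigator records on the SAE form, including "causality (i.e. relatedness to intervention), in the opinion of the investigator".

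Section 6.1 deals with adverse events in general. Those outside the exempt categories go on a special-interest form, and the possible examples given are "musculoskeletal injuries related to exercise, or adverse events during the conduct of physical outcomes assessments". The section sets no start or end date for that form.

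In the schedule (section 4.9), the row "6minute Walk Test" is marked at visits 1, 6 and 7: baseline, 3 months post EOT and month 24. The row "Adverse events / complications of treatment" is marked at visits 3, 4 and 5: cycle 2, cycle 3 and EOT. Section 4.4 fixes the order at the start: "Baseline assessments should also have been completed prior to randomisation".

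**The concern.** The walk test is an exertion test that the trial itself imposes on people who have just finished induction, or who have recently finished consolidation or transplant. The protocol recognises that such assessments can cause harm, because it names them in section 6.1. The period during which a serious event must be reported contains none of the occasions on which the test is scheduled, so the sufficiency statement in section 6.3.3 does not hold for this procedure.

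The late-report exception does not clearly close the gap. It depends on the word related, and the only meaning the protocol gives for that is relatedness to the intervention. A fall or cardiac event brought on by the walk test is caused by a trial procedure. An investigator completing the form as written could properly answer that it is unrelated to either package of care. The exception also looks only forward from the end of the period, so it cannot reach a test done before randomisation.

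What is at stake is safety oversight of a trial procedure, and the completeness of adverse events and SAEs, which section 2.2.2 lists among the secondary outcomes.

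**Working it through.** No power or alpha figure enters this point. The check sets the schedule against the reporting period.

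**Inputs**
- SAE period: randomisation to EOT + 30 days (section 6.3.3).
- Visits: section 4.9. Baseline precedes randomisation: section 4.4.
- Overall treatment can last up to 6 months (section 1.1). This appears to include induction, so taking all 6 months as randomisation to EOT is generous to the plan.
- Cycles of 4 to 6 weeks with gaps of 1 to 2 weeks (section 1.1); randomisation at least 8 days before cycle 1 (section 4.9, note a).
- One month = 365.25 / 12 = 30.44 days.

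**Step 1: marked visits**

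| Row in the schedule | Visits marked | Within randomisation to EOT + 30 days |
|---|---|---|
| 6-minute walk test | 1, 6, 7 | 0 of 3 |
| Hand grip strength | 1, 5, 6, 7 | 1 of 4 (EOT) |
| SARC-F and calf circumference | 1, 5, 6, 7 | 1 of 4 (EOT) |
| Adverse events | 3, 4, 5 | – |

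The walk-test visits {1, 6, 7} and the adverse-event visits {3, 4, 5} have no visit in common.

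**Step 2: distance from the period**
- Baseline: before randomisation, so before the period opens.
- 3 months post EOT: 3 × 30.44 = 91 days after EOT, against a cut-off of 30 days. 91 − 30 = 61 days after the period closes, whatever the length of treatment.
- Month 24: 24 × 30.44 = 730.5 days after randomisation. The distance depends on when EOT falls.

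| Course assumed | EOT (days) | Period closes (days) | Month-24 test falls later by (days) |
|---|---|---|---|
| Short: 8-day lead, two 4-week cycles, one 1-week gap | 8 + 56 + 7 = 71 | 101 | 629.5 |
| 6 months from randomisation | 182.6 | 212.6 | 517.9 |
| Long: 8-day lead, three 6-week cycles plus a 6-week HSCT cycle, three 2-week gaps | 8 + 168 + 42 = 218 | 248 | 482.5 |

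For the month-24 test to fall inside, EOT would have to be at day 730.5 − 30 = 700.5 or later, which is about month 23.

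**Step 3: what the text requires for a walk-test event**

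| Event | Special-interest form (6.1) | SAE form (6.3.3) |
|---|---|---|
| Non-serious, any of the three tests | Arguably yes; no period stated | Not applicable |
| Serious, baseline | Arguably yes; no period stated | Not required: before the period opens |
| Serious, 3 months or month 24 | Arguably yes; no period stated | Only if judged related, which 6.3.1 ties to the intervention |

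The last two rows are the gap. They concern the SAE form, which carries the 24-hour deadline in section 6.3.1 and feeds the report to the ethics committee in section 6.3.2.

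**The case against.** The strongest reply is that the period in section 6.3.3 governs SAEs only. Section 6.1 gives assessment harms a separate route with no time limit, and defines an adverse event by taking part in a study, not by randomisation. Under section 6.2 an SAE is a kind of adverse event, so a serious walk-test event is also within section 6.1. The schedule's adverse-event row fits routine collection during treatment and does not forbid an event-driven form at another visit. Section 6.1 also offers assessment events as an example of events possibly linked to delivery of the intervention or control, which suggests a broader sense of related than the form field in section 6.3.1.

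Much of this stands. A reader might infer that walk-test harms go unreported, or that nothing at all covers the baseline test. The documents do not support either, because section 6.1 can be read to cover both. Nor do they support the inference that such events would be kept from the DMC: section 9.9 does not tie what the committee sees to the SAE period.

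The reply does not rescue the SAE period itself. On the generous reading, a minor strain at month 24 is reportable without limit, while a serious event at the same test, judged unrelated to the intervention, need not go on an SAE form. The broader sense of related has to be inferred across sections, whereas the narrow one is written where the investigator makes the judgement. Even the broad sense leaves the baseline test before the SAE period.

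**Conclusion.** The point holds as an inconsistency among sections 4.9, 6.1, 6.3.1 and 6.3.3 that should be reconciled. None of the three scheduled walk tests falls inside the SAE period, and none coincides with a visit marked for adverse-event collection. Followed as written, the rules could miss serious procedure-related events on the SAE form: at baseline because of timing, and at 3 months and month 24 because of how causality is defined.

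The baseline and 3-month results need no assumption about treatment length. The month-24 result assumes EOT before about month 23, which section 1.1 makes safe. The finding is specific to the walk test, since grip strength, SARC-F and calf circumference are also measured at EOT, inside the period.

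Two stronger readings should be set aside. One is that the reported safety profile would favour an arm. The baseline test precedes allocation and both arms take the same later tests, so the effect is possible under-capture in both arms. The other is to size the problem as 600 × 3 = 1,800 tests. That is a ceiling before death, withdrawal and missed visits (section 8.1 allows for 20% dropout), and it counts tests, not harms. The protocol gives no rate of walk-test events, so the number of events missed cannot be estimated.

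**What to change.** Make these changes in one amendment:

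1. Sections 6.1 and 6.3.3: start reporting of SAEs and special-interest adverse events at the first trial-specific assessment after consent, and state the period for the special-interest form.
2. Section 6.3.3: state that any AE or SAE during or shortly after a physical outcomes assessment is reportable whenever it occurs.
3. Section 6.3.1: define causality as relatedness to the intervention, the control or trial procedures.
4. Section 4.9: mark the adverse-event row at baseline, 3 months post EOT and month 24, with a footnote limiting it to these events.
5. Section 6.3.3: correct the cross-reference for exempt SAEs. It points to section 7.2, which is Source Data; the list is in section 6.2.

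The cost is protocol wording, use of an existing form at three visits, and a few extra reports. No treatment, outcome or analysis changes.
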